PROTOCOL SHORT TITLE: Choose to Change – Reducing Tobacco Disparities

Protocol Title: **Reducing Tobacco Use Disparities Among Adults in Safety Net Community Health Centers**

Principal Investigators: [name]. (Lead PI)
Northwestern University
[contact]
[contact]

[name]. (Co-PI)
University of Illinois at Chicago
[contact]

[name]. (Co-PI)
Northeastern Illinois University
[contact]

[name]. (Site PI)
Near North Health Services Corporation
[contact]

[name]. (Site PI)
Alliance of Chicago

Biostatistician: [name].
Brown University
[contact]

Version Date: May 14, 2018

ClinicalTrials.gov
Registration Number: NCT03077737

PURPOSE OF STUDY & OBJECTIVES

An estimated 26 million smokers still receive no treatment for their smoking during their primary care visits. Given the persistent clinical system, provider, and patient barriers to addressing smoking, especially among poor populations, an EHR-automated population health management approach that links a healthcare system with community services both clinically and electronically to engage all smokers may increase access to effective treatment. Increased access is especially significant for low-income smokers who are underserved and carry a disproportionate burden of tobacco-related disease. This 2-group randomized controlled trial will evaluate the effectiveness of a person-centered population health management intervention for smoking cessation in low-income smokers. The following aims and hypotheses will be tested:

Primary Aim 1 (Effect on Treatment Engagement): Compare Choose to Change versus Usual Care for engaging low-income smokers in treatment. Hypothesis: Choose to Change will increase the proportion of smokers who complete a behavior counseling call by 6 weeks (24%), compared with Usual Care (10%).

Primary Aim 2 (Effect on Treatment Utilization): Compare Choose to Change versus Usual Care for increasing treatment utilization. Hypothesis: Choose to Change will increase the proportion of smokers who complete ≥ 1 additional behavior counseling calls by 14 weeks (15%), compared with Usual Care (7%).

Primary Aim 3 (Effect on Smoking Cessation): Compare Choose to Change versus Usual Care for increasing smoking cessation. Hypothesis: Choose to Change will increase the proportion of smokers

PROTOCOL SHORT TITLE: Choose to Change – Reducing Tobacco Disparities

abstinent at 28 weeks (7%), as defined by bio-verified 7-day point-prevalence abstinence, compared with Usual Care (2%).

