Five hundred thirty adult male and female English- or Spanish-speaking current smokers who are patients at one of seven federally qualified health centers (FQHC) within the Near North Health Services Corporation (NNHSC) community clinic system will be enrolled in this clinical trial.

Inclusion Criteria

Eligible participants will be males and females who are:

1. 18 years of age or older;
2. A patient at one of the seven participating NNHSC community clinics;
3. Listed as “current someday smoker” or “current everyday smoker” in their NNHSC EHR; confirms current someday or everyday smoking status at phone screen
4. Have had ≥ 1 visit to their NNHSC clinic within the past 12 months

Exclusion Criteria

Participants who self-report any of the following will not be eligible to participate in the study:

1. Documented within their NNHSC EHR as preferring a language other than English or Spanish for healthcare;
2. No telephone number or address listed in the EHR;
3. Does not have a cell phone with texting capabilities;
4. Lives with another NNHSC patient who is already enrolled in the present study.

[figure not shown]
Vulnerable Populations

Children under 18 years of age, fetuses, neonates, or prisoners will not be included in this study. Pregnant women will not be actively recruited, but will be eligible for the study if they meet all other inclusion and exclusion criteria detailed above.

STUDY DESIGN

This is a 2-group randomized controlled trial to evaluate the effectiveness of the population health management intervention for low-income smokers that aims to promote Quitline treatment, engagement, utilization, and smoking cessation (Figure 1).

Figure 1. Study Design

Length of Study Participation

PROTOCOL SHORT TITLE: Choose to Change – Reducing Tobacco Disparities

Participants will be involved in study-related activities for approximately 7½ months (32 weeks) from initial enrollment in the observational study and baseline assessment (week -4) through follow-up (week 28). Participants will complete four phone-based assessments during this time (Baseline/Week -4; Week 6; Week 14, Week 28) and those who report abstinence from cigarettes at the Week 28 phone interview will be asked to come in for an in-person clinic visit within 2 weeks of their Week 28 phone session in order to bioverify smoking status.

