The EHR query to identify participants will also generate information on the following characteristics: sociodemographic (age, gender, race, ethnicity, marital status, household income, education), smoking history (number of years smoking, past year quit attempts, use of multiple tobacco products, past referral for smoking cessation treatment, including quitline), and healthcare (e.g., date of last clinic visit, type of health insurance, most recent problem list). A second query will be run at the 8-month time point to generate number, dates, purpose of any clinic visit(s) during the study period, whether or not smoking was addressed (a required field in the EHR system), and an updated problem list.

Characterization of Population that Engages in Quitline Treatment

Participants who accept the Quitline call will complete a registration process that includes brief assessment of smoking and smoking history to guide treatment. Information will be obtained on current smoking, including frequency and preference for menthol cigarettes. If non-daily smoking is endorsed, counselors will ask about a typical smoking day. If daily smoking is endorsed, cigarettes per day and time to first cigarette will be obtained. Counselors also ask about how long the participant has been a smoker, number of past quit attempts and, if any, by what method.

Telephone Surveys on Health Behaviors

Because many outcome, moderator, mediator, and control variables cannot be received from the Quitline via the EHR system for participants who do not engage in Quitline treatment, enrolled participants will complete the “NNHSC Health Habits and Wellness service needs survey” of smoking status and moderator, mediator, and control variables via telephone interview at baseline (week -4; 4 weeks before randomization to treatment and letter mailing), 6, 14, and 28 weeks.

Treatment Outcomes

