Treatment engagement will be measured at 6, 14, and 28 (as applicable) weeks after letter mailing, and operationalized as the proportion of participants who accept the proactive Quitline call and accept treatment as defined by completing the counseling session. Participants who return a Quitline call and accept treatment also will be counted as having engaged in treatment. Further, we will assess: 1) the proportion of smokers who request cessation versus reduction counseling; and 2) the proportion of smokers who engage in treatment and who request NRT and (or) schedule a follow-up (proactive or reactive) counseling call.

Treatment utilization will be measured at 6, 14, and 28 (as applicable) weeks and will be defined as the proportion of participants who complete ≥ 1 additional counseling calls and receive and use NRT. The frequency and duration of sessions will also be measured.

Smoking cessation at 6 and 14 weeks will be defined as self-reported abstinence (not even a puff of a cigarette) for ≥ 7 days. At 28 weeks, breath CO will be used to verify abstinence for participants in the original study timeline. For participants in the alternative shorter study timeline, breath CO will be measured at 14 weeks to verify abstinence. Participants will be classified as abstinent if they report not smoking (not even a puff of a cigarette) for ≥ 7 days and have a CO ≤ 8 parts per million (ppm). Participants will be assumed to be smoking if they report smoking, cannot be reached to provide data, fail to provide a breath sample, or provide a breath sample that is >8 ppm.¹⁰⁵ Participants who report abstinence at 28 weeks (original timeline) or 14 weeks (alternative shorter timeline) will be invited for an in-person visit for breath carbon monoxide (CO) measurement to bio-verify abstinence status.

Moderators, Mediators, and Covariates

Hypothesized moderators of Choose to Change effects will be measured at baseline and include readiness to quit smoking,^{96,97} recent smoking reduction,⁵¹ cigarettes per day, time since last clinic visit during which smoking was addressed, initial choice of cessation versus reduction, race/ethnicity, perceived stress, , and discrimination. Hypothesized mediators of intervention effects on treatment engagement, utilization, and cessation will be measured at each survey time point and will include perceived autonomy support, autonomous motivation, confidence in ability to quit, and attitude towards NRT.

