Demographic Questionnaire: Age, gender, ethnicity, and race will be measured only at baseline. Current regular smoking (daily or weekly), NHHSC home clinic for primary health care, and residential address will be confirmed. Participant residential addresses and telephone numbers will be confirmed at the baseline

PROTOCOL SHORT TITLE: Choose to Change – Reducing Tobacco Disparities

assessment prior to treatment randomization to verify that the address in the EHR is accurate. This will help ensure that the participant receives the Choose to Change letter. Residential and email addresses will be confirmed at each survey.

Health Behaviors Assessment: This questionnaire will assess diet, alcohol use, physical activity, sedentary behavior, perceived stress, cigarette smoking/recent treatment (including Quitline treatment) and motivation to quit, and current desire for various health promotion services. Past week physical activity and sedentary behavior will be measured using the International Physical Activity Questionnaire short form. Health Information National Trends Survey (HINTS) items were used to assess fruit, vegetable, and sugar-sweetened beverage consumption. Alcohol consumption over the past 30 days will be assessed using the two-item PhenX Alcohol Use module. Perceived Stress will be assessed with the 4 -item Perceived Stress Scale will be used to measure general stress experienced over the last month.

Perceived Autonomy Support: The Health Care Climate Questionnaire consists of six statements that respondents must indicate the degree to which they experience their health care provider(s) as autonomy supportive versus controlling. Each HCCQ statement is scored on a 7-point Likert scale (1=Not at all True, 7=Very True). E.g., “I feel that my health-care practitioners have provided me with choices and options about smoking (including not quitting).”

Attitudes Towards Nicotine Replacement Therapy Scale (ANRT): The ANRT is a 12-item scale consisting of two subscales measuring the perception of the advantages of NRT (8-items) and drawbacks (4-items) of nicotine replacement therapy to quit smoking. “Advantages” taps beliefs that NRT will provide relief from withdrawal and craving during cessation, and “drawbacks” describes concerns about NRT dependence, side-effects, and efficacy. Scores have been associated with intention to use NRT, prior NRT use, nicotine dependence, and among those who have ever used NRT, the number of days of use.

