Our power estimates for **Aim 2 (Treatment Utilization at 14 Weeks)** will be based on Williams et al.⁹ who reported a 30% utilization rate for combined counseling and medication at a later time point than ours (6 months), following a face-to-face SDT-based intervention. Assuming 6-month utilization rates (one or more counseling calls after the initial counseling call) for the Usual Care and Choose to Change conditions of **7%** and **15%**, respectively, would be consistent with their treatment utilization odds ratio of 2.38 (95% CI=1.67-3.39), albeit at a lower baseline rate than they report. Our proposed randomization plan guarantees **84% power** for the comparison of Usual Care versus Choose to Change at two-sided alpha=.05.

Our power estimates for **Aim 3 (Smoking Cessation at 28 Weeks)** will be based primarily on Rigotti et al.²⁷ who reported 7-day point-prevalence abstinence rates at 14 weeks of 1% for standard care and 5% for population mail outreach under an Intent-to-Treat (ITT) approach. We expect that these 12-week ITT rates will rise to 3% in our Usual Care condition and 10% in the Choose to Change condition. Even if these rates then drop to **2%** in our Usual Care and **7%** in Choose to Change at 26 weeks, we still have **80% power** for the comparison of Choose to Change versus Usual Care at two-sided alpha=0.05.

Data Analysis

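### The minimum smoking frequency at entry is stated in two ways, and smokers with smoke-free weeks can count as abstinent without quitting; any loss of Aim 3 power is conditional

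*Combined protocol and SAP*

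**What the plan says.** **Entry.** Under Inclusion Criteria, the patient must be listed in the EHR as a someday or everyday smoker and be someone who "confirms current someday or everyday smoking status at phone screen". No minimum frequency is given. Under Measures, the Demographic Questionnaire says: "Current regular smoking (daily or weekly), NHHSC home clinic for primary health care, and residential address will be confirmed". The section places this at the baseline assessment, before randomisation. It does not call the item an eligibility criterion, and it does not say what happens if regular smoking is not confirmed.

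**Non-daily smokers are expected.** The section on participants who engage with the Quitline says: "If non-daily smoking is endorsed, counselors will ask about a typical smoking day".

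**Outcome.** Treatment Outcomes says: "Participants will be classified as abstinent if they report not smoking (not even a puff of a cigarette) for ≥ 7 days", together with a breath CO of 8 ppm or less at week 28 (week 14 on the shorter timeline). Participants who are not reached or give no breath sample count as smoking. Nothing requires smoking in the 7 days before baseline.

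**Planned rates and analysis.** Table 3 gives assumed intent-to-treat cessation rates of 2% and 7% with 265 participants per arm, and Power states 80% power at two-sided 0.05. The starting point was a cited mail-outreach trial with "7-day point-prevalence abstinence rates at 14 weeks of 1% for standard care and 5% for population mail outreach". The plan does not say which smoking frequencies the 2% and 7% cover. Randomisation is stratified by readiness to quit, race and language. The primary logistic regression names no adjustment for smoking frequency. Smoking level appears only in the exploratory moderator models.

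**The concern.** A person who smokes less than once a week passes the phone screen but does not fit the description in the questionnaire. With no stated consequence, staff could handle the same patient in different ways.

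If such people are enrolled, the endpoint cannot tell them from quitters. Someone who ordinarily has smoke-free weeks can truthfully report 7 days without a puff. CO verification confirms that they have not smoked recently, not that they changed.

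The planned rates are low enough for this to matter. Usual Care expects 0.02 × 265 = 5.3 quits, and one extra percentage point is about 2.65 people per arm, half that number. Secondary Aim 1 divides cost by successful quits, so people who did not change would also enter that denominator.

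**Working it through.** **1. The plan's own figure.** Inputs from Power and Table 3: p1 = 0.02, p2 = 0.07, n = 265 per arm, two-sided alpha 0.05. Pooled two-proportion test:

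power = Φ[(d − 1.96·se0)/se1], with se0 = √(2·p̄(1−p̄)/n) and se1 = √([p1(1−p1) + p2(1−p2)]/n).

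Here p̄ = 0.045, se0 = 0.01801 and se1 = 0.01788, so (0.05 − 0.03530)/0.01788 = 0.822 and power = 79.5%. The same formula gives 99.1% for Aim 1 (stated 99%) and 83.9% for Aim 2 (stated 84%), so it appears to be the method used.

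**2. Adding non-quit abstinence.** Let b be the share of participants, equal in both arms, who meet the definition without quitting. The documents give no value for b, so it is an assumption. If b applies to those not otherwise abstinent, each rate becomes p + b(1 − p). For b = 2 points the rates are 0.0396 and 0.0886, d = 0.0490, se0 = 0.02128 and se1 = 0.02117, which gives 63.5%. The last column keeps the difference at exactly 5 points.

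| b (points) | Usual Care | Choose to Change | Power | Power, exact 5-point difference |
|---|---|---|---|---|
| 0 | 2.00% | 7.00% | 79.5% | 79.5% |
| 0.5 | 2.49% | 7.47% | 75.1% | 75.3% |
| 1 | 2.98% | 7.93% | 71.0% | 71.5% |
| 2 | 3.96% | 8.86% | 63.5% | 64.7% |
| 3 | 4.94% | 9.79% | 57.1% | 58.9% |

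If 2% and 7% already include such smokers, the first row applies.

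**3. What the remedies recover.** Example, both inputs assumed: 10% of participants smoke less than weekly, and each has a 20% chance of a smoke-free week, so b = 2 points. Simulated power, with true quitting at 2% and 7% throughout:

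| Analysis | Power |
|---|---|
| All randomised, unadjusted | about 65% |
| All randomised, stratified by less-than-weekly or not | about 67–68% |
| Only those who smoked in the 7 days before baseline | about 67% |
| Only those classed at baseline as at least weekly | about 78% |

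Simulated figures run slightly above the formula. By exact enumeration the uncontaminated trial has 82% rather than 79.5%, and by formula the last row is about 75% (238 per arm at 2% and 7%). Rows should be compared only within the table.

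The third row is low because, when smoke-free weeks are independent, 80% of the less-than-weekly smokers did smoke in the week before baseline and stay in.

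Stratifying by everyday versus someday gains the same 3 points or so only if the someday group consists of less-than-weekly smokers. If a further 10% of participants (assumed) are someday smokers who smoke weekly, the simulated gain is about 1 point.

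**4. Cost per quit, same b = 2 points.** Usual Care: 5.3 true quits plus 265 × 0.02 × 0.98 = 5.2 others, so about half of the counted quits are not quits. Choose to Change: 18.6 true quits plus 265 × 0.02 × 0.93 = 4.9 others, about 21% of those counted. An average cost per quit is understated in both arms, and more so in Usual Care. The between-arm difference in quits barely moves (13.25 to 12.99).

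**The case against.** **The questionnaire item is not an exclusion.** This stands. A reader might infer that less-than-weekly smokers are eligible in one section and barred in another, but the second section lists a confirmation, not a criterion. If the item does in fact control entry, such smokers are not enrolled and most of the endpoint problem disappears. Either way, the text does not say.

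**The power loss is not in the documents.** This also stands. Table 3 labels the rates as intent-to-treat assumptions for the trial population, which may already include someday smokers. If the odds ratio of 3.69 were constant instead of the difference, power would rise to 92.0% at 1 added point. That would require the intervention to multiply abstinence unrelated to treatment: at 5 added points it implies 7% against about 22%, where the plan assumes a 5-point effect.

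**The protocol limits the numbers.** An unchanged occasional smoker must be reached, report abstinence, attend in person and pass the CO test. In the example, the 75% reach expected under Data Analysis cuts b from 2 to 1.5 points (67% power by formula). An assumed 50% attendance cuts it to 0.75 points (73%). This shrinks the problem but does not remove it, because those who attend still cannot be told from quitters.

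**Smoking level is already modelled, and someday smokers fit an outreach trial.** Both are true, but the moderator models are exploratory. The proposal keeps someday smokers in the primary population.

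**Conclusion.** Two things follow from the text alone. The entry requirement is described in two ways that must be reconciled, and the abstinence definition can be met by a less-than-weekly smoker who has not changed. Neither the stratification nor the primary Aim 3 model uses baseline smoking frequency.

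A reader might go further and conclude that the stated 80% power is wrong or already eroded. The documents do not support that: the figure reproduces at 79.5%. The fall to about 75%, 71%, 64% or 57% requires that 2% and 7% exclude such smokers, that the absolute effect is essentially unchanged, and that 0.5, 1, 2 or 3 points of non-quit abstinence occur in both arms. None of these is stated.

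A reader might also expect that restricting the analysis to people who smoked in the week before baseline would restore the power. In the worked example it recovers only about 2 points.

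If the planned rates already include these smokers, power is unaffected, but some counted quits are still not quits, and an average cost per quit is understated.

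**What to change.** 1. Reconcile the Inclusion Criteria with the Demographic Questionnaire. State whether daily or weekly smoking is a condition of randomisation and what happens when it is not confirmed. Which rule applies is for the investigators to decide.
2. State under Power whether 2% and 7% include less-than-weekly smokers. If they do not, present the power as conditional on b.
3. Adjust or stratify the primary Aim 3 logistic regression for baseline everyday versus someday smoking. The status is in the EHR and confirmed at screening, so the cost is SAP wording. In the worked example the gain is at most about 3 points, and smaller if many someday smokers smoke weekly.
4. Pre-specify a sensitivity analysis of Aim 3 and of cost per quit, limited to participants classed at baseline as smoking at least weekly. The group is defined before randomisation, so the comparison stays randomised. The baseline item must record frequency for everyone, and the sponsor should confirm that it does.

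The sensitivity analysis drops the less-than-weekly smokers, whom the outreach may also be meant to reach. All randomised participants should therefore remain the primary population.

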Alternative study timeline: Due to funding constraints, participants enrolled February 2018 or after will be involved in study-related activities for about 4 months (18 weeks) from initial enrollment in the observational study and baseline assessment (week -4) through a final follow-up at week 14. Participants enrolled in this alternative study timeline will complete three phone-based assessments (Baseline/Week -4; Week 6; Week 14) and those who report abstinence from cigarettes at the Week 14 phone interview will be invited to come in for an in-person clinic visit within 2 weeks of their Week 14 phone session in order to bioverify smoking status. Randomization to treatment arm and all other study procedures will be conducted in the same way as for the participants completing the full 32 week study timeline.

Study Timeline

Development of Bilateral EHR Interface with the Quitline. Led by Drs. [name] and [name], we will complete the testing and refinement of the bilateral EHR interface between NNHSC and the Quitline. Trainings with providers in use of the new EHR functionality will also be conducted. The integration of NNHSC and the Quitline will enable the NNHSC study care coordinator and providers to make a one-step referral to the Quitline. In turn, the Quitline will communicate patient outcomes directly to NNHSC via the EHR. The existing EHR content will be modified to automate obtaining and documenting provider approval of patient involvement and generating and documenting the mailing of the intervention letters. All clinical information will be communicated to the Quitline using Health Level Seven (HL7) standards. The Quitline will use a HL7 interface engine to receive and “translate” the information within its secure network.

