PROTOCOL SHORT TITLE: Choose to Change – Reducing Tobacco Disparities

- 8) Sending seasonal newsletters about living a healthy lifestyle;
- 9) Demonstrating a positive and caring attitude towards participants¹⁰⁹;
- 10) Rapid rescheduling of missed appointments; and
- 11) Acknowledgement and appreciation of participant effort.

These enrollment and retention strategies have been effective in pragmatic clinical trials and community studies of underserved populations,¹¹²⁻¹¹⁵ as well as in our ongoing cohort study (N01 HC48049).

STATISTICAL ANALYSIS PLAN

Power

To address power for hypotheses related to **Aim 1 (Treatment Engagement at 6 Weeks)**, we base our estimates for the proportion of participants completing a Quitline session by 6 weeks in the Choose to Change condition on our pilot study that resulted in a **24%** engagement rate. As for the Usual Care condition, we expect that current NNHSC Ask, Advise, Refer practice involving the Quitline as the primary referral program will result in a tripling to **10%** of the 3.3% engagement rate achieved in our EHR fax-referral project, in which our NIH-funded study of long-term nicotine patch treatment, with inclusion and exclusion criteria, served as the primary referral program.⁹⁴ Assumed rates by condition for each of the three outcomes of interest and participants per condition are presented in Table 3. We propose that a minimum of N=265 independent participants be randomized to Choose to Change versus N=265 to Usual Care, for a total N=530. Such a 1:1 allocation ratio guarantees **99% power** for the comparison of Choose to Change versus Usual Care at two-sided alpha=.05. This sample size requirement equates to 40 participants per month over the 15-month randomization period. In our three-week pilot study, 132 patients were processed through the workflow in Figure 3, a rate of 175 per month.

Table 3. Assumed Intent-to-Treat Rates by Condition for the Three Outcomes of Interest and Participants per Condition

Study Aim	Usual Care	Choose to Change
Aim 1: Engagement (6 Weeks)	10%	24%
Aim 2: Utilization (12 Weeks)	7%	15%
Aim 3: Cessation (26 Weeks)	2%	7%
Participants	265	265

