All outcomes of interest for **Primary Aims 1-3** are binary (treatment engagement, treatment utilization, smoking cessation) and can be analyzed using logistic regression methods. Analyses will be conducted first using an ITT principle (missing=treatment failures). We will also conduct an adherence sample analysis that includes only participants reached at the 28-week follow-up ($\geq 75\%$ of the sample based on our experience). This approach addresses the question of effectiveness more directly, but it is subject to more bias if attrition is large or differential by treatment condition. Therefore, we will complement it by analysis of non-response patterns using sociodemographic (age, gender, race, ethnicity, marital status, household income, education), and healthcare (time since last clinic visit, type of health insurance) characteristics. These can be used to create propensity scores that allow for inverse-probability-weighting (IPW) of observed outcomes^{116,117} to achieve balance across potential confounders of the treatment-to-outcome relationship. Ideally, the distribution of propensity scores will show large overlap across study conditions. If not, that will be taken as evidence that completers are not comparable on measured confounders across conditions, and that one should refrain from

PROTOCOL SHORT TITLE: Choose to Change – Reducing Tobacco Disparities

further comparisons. PROC GENMOD of SAS/STAT 9.2¹¹⁸ can handle subject-level probability weights. Similar findings across all three approaches would increase confidence in the results overall. Both raw and adjusted rates will be presented for each outcome by study condition. For the cessation outcome, we will also explore the impact of smoking history (e.g., past year quit attempts, past referral for Quitline treatment), race, and gender on non-response. We will also use propensity score modeling to examine the relationship between treatment utilization at 14 weeks and abstinence at 28 weeks. Since available data indicate little effect of NRT type on outcome, we will model NRT dose/duration, while controlling for patterns of utilization.

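### Aim 3 is still defined, powered and analysed at week 28, although participants enrolled from February 2018 finish at week 14 and the SAP has no rule for them

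*Combined protocol and SAP*

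**What the plan says.** - Aim 3 (Purpose of Study & Objectives) concerns participants "abstinent at 28 weeks (7%), as defined by bio-verified 7-day point-prevalence abstinence, compared with Usual Care (2" percent).
- Study Design, Alternative study timeline: "participants enrolled February 2018 or after will be involved in study-related activities for about 4 months (18 weeks", with week 14 as their final follow-up.
- Measures, Treatment Outcomes: "For participants in the alternative shorter study timeline, breath CO will be measured at 14 weeks to verify abstinence". For the original timeline CO is taken at week 28, and the general rule is that "Smoking cessation at 6 and 14 weeks will be defined as self-reported abstinence".
- Statistical Analysis Plan, Power: "a minimum of N=265 independent participants be randomized to Choose to Change versus N=265 to Usual Care". The Aim 3 power of 80% is "for the comparison of Choose to Change versus Usual Care at two-sided alpha=0.05" and assumes 2% v 7%. That paragraph is headed 28 weeks, but its rates, like the Table 3 row "Aim 3: Cessation (26 Weeks", are labelled 26 weeks.
- Statistical Analysis Plan, Data Analysis: "Analyses will be conducted first using an ITT principle (missing=treatment failures"). It also plans an adherence-sample analysis of those reached at week 28 (expected to be at least 75% of the sample), a non-response analysis on listed sociodemographic and healthcare variables, and a model relating week-14 utilization to week-28 abstinence.

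The Statistical Analysis Plan does not mention the shorter timeline anywhere. The cut-off for it also differs within the protocol: the start of February 2018 in Study Design, mid-February 2018 under Study Subject Compensation.

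**The concern.** The shorter timeline was carried into measurement, retention, consent and compensation, but not into the primary aim or its analysis. Two readings are open.

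(a) Strict week 28. Later enrollees have no week-28 visit. The missing-data rule has no exception for visits that were never scheduled, so these participants are counted as smokers or, if set aside, lost from the comparison.

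(b) Final scheduled visit. The week-14 CO result counts for later enrollees. The reported figure then blends 14- and 28-week abstinence and is not the endpoint that Aim 3 states.

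Week 14 cannot serve as a common verified endpoint, because abstinence at that visit is self-report only in the original cohort.

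This is a primary endpoint, and the text leaves both the outcome and the analysis set to be chosen later. Under (a) the effect is diluted and power is lost. Under (b) power is roughly kept but the question answered has changed. As written, the secondary analyses do not fit the short cohort either: the adherence set excludes all of it, the listed non-response variables include neither timeline nor enrolment date (so a calendar cut-off would be modelled as attrition), and the utilization-to-abstinence model has no outcome for it.

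**Working it through.** **Inputs.** From the Power section and Table 3: n = 265 per arm, two-sided alpha 0.05, and 2% v 7% for Aim 3. The Power section also gives expected 12-week rates of 3% v 10%, and 1% v 5% from the cited mail-outreach trial. Accrual of 40 per month is from Participant Recruitment. The short-timeline share f is not in the documents and is varied from 5% to 50%.

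**Formula.** Two-proportion z-test with pooled null variance and p̄ = (p1 + p2)/2:

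power = Φ{ [ |p2 − p1| − 1.96·√(2p̄(1 − p̄)/n) ] / √( [p1(1 − p1) + p2(1 − p2)]/n ) }

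**The plan's figure.** For 2% v 7%, p̄ = 0.045. The null SE is √(2 × 0.045 × 0.955/265) = 0.01801 and the alternative SE is √((0.0196 + 0.0651)/265) = 0.01788. Then (0.05 − 1.96 × 0.01801)/0.01788 = 0.822, and Φ(0.822) = 79.5%. The same formula gives 99.1% for Aim 1 (stated 99%) and 83.9% for Aim 2 (stated 84%). The stated 80% is therefore right, provided all 530 contribute a week-28 outcome.

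**Scenarios**
- (a) coded as failure: rates 2%(1 − f) v 7%(1 − f), n = 265.
- (a) excluded: 2% v 7%, n = 265(1 − f).
- (b) final visit: (1 − f)(2%, 7%) + f × (short-cohort rates), n = 265. The short-cohort rates are 3% v 10% or 1% v 5%. The plan does not say that the 3% and 10% are CO-verified.

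| f | Difference under (a), coded as failure | (a) coded as failure | (a) excluded | (b) 3% v 10% | (b) 1% v 5% |
|---|---|---|---|---|---|
| 0 | 5.0 points | 79.5% | 79.5% | 79.5% | 79.5% |
| 5% | 4.75 | 77.3% | 77.4% | 80.2% | 79.3% |
| 10% | 4.5 | 74.9% | 75.1% | 80.9% | 79.1% |
| 20% | 4.0 | 69.7% | 70.1% | 82.3% | 78.8% |
| 30% | 3.5 | 63.6% | 64.3% | 83.6% | 78.5% |
| 50% | 2.5 | 49.2% | 50.1% | 86.0% | 78.0% |

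Example at f = 20%, coded as failure: 1.6% v 5.6%, p̄ = 0.036; (0.04 − 1.96 × 0.01618)/0.01609 = 0.515; Φ(0.515) = 69.7%.

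**Scale of f.** At the planned rate, one short-timeline month is 40/530 = 7.5% of the sample and gives about 76% under (a).

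**Exact check.** Full enumeration of the pooled z-test gives 82.0% for the plan and, coded as failure, 79.9%, 77.6%, 72.5%, 66.6% and 50.7% at f = 5%, 10%, 20%, 30% and 50%. With 2%(1 − f) in both arms, exact type I error is 0.047 at f = 0, 0.045 at 30% and 0.046 at 50%.

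**Adherence set.** At most 1 − f of those randomized can be reached at week 28, so 75% is out of reach once f exceeds 25%, even with no loss to follow-up. If 75% of those scheduled are reached, the set is 0.75(1 − f): 60%, 52.5% and 37.5% of all randomized at f = 20%, 30% and 50%.

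**Cut-off mismatch.** Half a month × 40 = 20 people; 20/530 = 3.8%.

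**The case against.** The strongest reply is that Treatment Outcomes already points to reading (b). It gives a CO time for each timeline and one abstinence rule for both. Its presumption of smoking covers people who cannot be reached or give no breath sample, which describes failed contact and not an unplanned visit. Verifying abstinence at week 14 would have little purpose if the whole cohort were then coded as smoking. On that reading power is essentially kept.

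This makes (b) the likelier intention, but it does not close the gap. Nothing says that the week-14 result enters the Aim 3 comparison, whether the cohorts are pooled, or whether timeline is adjusted for. The stated endpoint also remains 28 weeks.

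Other points stand in part:
- f is unknown, so only the direction and a range can be shown. At f = 5% the exact calculation still rounds to 80%; a clear fall needs roughly 10% or more.
- The non-response problem disappears if non-response is judged at the final scheduled visit. The plan instead defines the completer set by week 28.
- The adherence, weighting and utilization analyses are complementary to the primary ITT comparison.
- Aims 1 and 2, at 6 and 14 weeks, lie within both timelines and are unaffected.
- The 26/28-week labels and the date mismatch change no power calculation and carry little weight.

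**Conclusion.** The concern holds and should be fixed. The missing analysis rule is certain from the text. The power loss is conditional on reading Aim 3 strictly at week 28 and on the unstated f. Under that reading the 5-point difference shrinks in proportion to f if unscheduled visits are coded as failures; excluding the cohort leaves the difference intact but costs nearly the same power. Because the plan starts at about 80%, it has no margin to absorb either.

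The dilution is the same in both arms, so the cost is in power and effect size and not in false positives. Using each cohort's final visit avoids most of the loss under the plan's own rates, at the price of an endpoint other than the one stated. All these figures assume the planned rates, 265 per arm and equal short-timeline shares in the two arms.

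**What to change.** 1. State that missing counts as smoking only for assessments the participant was scheduled to have.
2. Define the Aim 3 outcome for each timeline. One option is CO-verified 7-day abstinence at the final scheduled follow-up (week 28 original, week 14 alternative), with timeline cohort as a covariate, plus week-28 abstinence in the original cohort with power restated for the number scheduled to week 28. If week 28 in the original cohort is preferred as primary, say so and restate its power.
3. Base the completer and inverse-probability-weighted analyses on the final scheduled visit, and limit the week-14 utilization to week-28 abstinence model to the original cohort.
4. Use one cut-off date in Study Design and Study Subject Compensation, and one horizon label (26 or 28 weeks) across Aim 3, the Power section and Table 3.

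The cost is protocol and SAP wording only, since CO at each cohort's final visit is already planned. The downside cannot be avoided: either the primary endpoint mixes two horizons, or the power for a pure 28-week endpoint is lower than stated. The choice should be fixed before outcomes are compared by arm.
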